## METHODS

### PARTICIPANTS

Patients with CVD that underwent to a hospital-based CR program in the Lisbon district Hospitals will be recruited. The study will be performed in the Cardiovascular Rehabilitation Center of the University of Lisbon (CRECUL) at the Lisbon University Stadium (EUL). The participants will be randomized into one of the following exercise groups: 1) periodized group; 2) non periodized group following the American College of Sports and Medicine (ACSM) guidelines. Patient's eligibility will be assessed according to the risk stratification criteria for patients with CVD for low and/or moderate risk stratification from the American Association of Cardiovascular and Pulmonary Rehabilitation. Male and female participants, ≥ 18 years of age, who had an established history of the following conditions or procedures will be included: MI, or coronary revascularization (coronary artery bypass grafting, percutaneous transluminal coronary angioplasty, or coronary artery stent), angina pectoris or coronary artery disease defined by angiography. Exclusion criteria

will be participants who had heart failure, heart transplants with either cardiac resynchronization therapy or implantable defibrillators; inability to comply with guidelines for participation in exercise testing and training; and significant limiting and/or unstable comorbidities that would prevent full participation.

Sample size was calculated (G-Power, *Version 3.1.3*) assuming a difference in peak oxygen uptake (VO2 peak) between groups of 3 ml/kg/min to be a clinically important difference with a SD of 3.5 ml/kg/min,  $\alpha=0.05$ ,  $1-\beta=0.80$  and an expected dropout rate of 37%. The calculations yielded a total minimum sample size of 50 participants (25 in each group).

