## PURPOSE

To overcome the lack of knowledge regarding the physiological effects after hospital-based CR program, a 12 month RCT study will be performed. This study will hopefully contribute to generate evidence-based exercise prescription approaches to prolong the ET after the end of hospital-based CR programs.

The purpose of this research project is twofold:

1) To conduct a 12-month randomized control trial to evaluate the effects of periodized ET regime versus a non periodized ET regime on VO2 peak, maximal strength, body composition, functionality and quality of life in CVD patients.

2) to differentiate the effects of a 12-month periodized ET regime versus a non periodized ET regime on the different components of the oxygen kinetics response and oxidative adaptations in CVD patients.

The primary end points for aim 1 are: cardiopulmonary exercise testing (CPET) variables such as VO2 peak, AT, peak work rate, ventilatory equivalent of carbon dioxide (VE/VCO2), ventilatory equivalent of oxygen (VE/VO2), minute ventilation (VE), one repetition maximum (1RM), total body bone mineral content, lean and fat tissue mass and percentage of body fat mass, quality of life and functional physical fitness tests. The primary end points for aim 2 are oxygen kinetics and muscle deoxygenation dynamics of the vastus lateralis muscle at the submaximal test.

The hypothesis for this study are: 1) considering that this type of periodization exerts higher stress on the cardiovascular and neuromuscular systems, so that there could be greater adaptations, leading to higher increases in VO2max, muscle strength, body composition and functionality compared to non periodized ET regime; 2) there will be a better improvement microvascular O2 delivery in the exercise transient in response to periodized ET regime that would be associated with a faster adjustment of pulmonary VO2 kinetics than in non periodized group. Improvements in microvascular O2 delivery would be indicated by a better matching between the rate of adjustment of muscle deoxygenation relative to phase II pulmonary VO2, which represents a decreased reliance on O2 extraction for a given pulmonary VO2.

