### 13. STATISTICAL ANALYSIS

Data will be analyzed in M0, M1, M2 and M3. It will be tested the data for normality and homogeneity of variance with the Shapiro Wilk and Levene's tests, respectively. Data analysis will be described according to the established purposes for this project (descriptive values: mean, standard deviation, range, % change) and comparisons of means will be used for all purposed outcomes intra and inter groups. Baseline characteristics between groups will be evaluated with oneway ANOVA. Mixed between within subjects ANOVA will be conducted in a 2 (pre vs post ET) design to assess efficiency of the program. When a significant interaction is observed, t tests, or Wilcoxon signed-rank tests will be used to determine where the interaction occurred.

M0 versus M1, M0 versus M2, M0 versus M3, M1 versus M2, M2 versus M3 and M1 versus M3 will be compared to evaluate the changes in patients and trace the necessary timespan for such changes using General Linear Mixed Model Analysis for repeated measures with Tukey's posthoc procedure for the mean comparisons. Pearson product moment correlation coefficient or Spearman's rank correlation coefficient will be used to study the relationship between different variables by group and correlation coefficients will be compared between groups. Statistical significance will be set at an alpha level of 0.05. Other statistical procedures can be done.

Statistical analyses will be conducted using Statistical Package for the Social Sciences (SPSS) 22.0 (IBM SPSS Statistics, Chicago, IL, USA).

Data analysis will allow peer reviews redaction, slide presentations and oral communications in national and international conferences at the end of 2017 beginning of 2018.

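### Fifty randomised with 37% dropout does not give the stated 80% power for VO2 peak: about 32 completers give 62-65% two-sided (74-77% one-sided).

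*Combined protocol and SAP*

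**What the plan says.** The only sample size justification is in Methods, Participants. It takes a VO2 peak difference "between groups of 3 ml/kg/min to be a clinically important difference", "with a SD of 3.5 ml/kg/min", alpha 0.05 and power 0.80, "and an expected dropout rate of 37%. The calculations yielded a total minimum sample size of 50 participants (25 in each group"). The software is named. The test, its sidedness, any correlation between visits and the rule for dropout are not. Nor does the paragraph say whether 3.5 is the SD of VO2 peak or of its change.

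Section 13 (Statistical Analysis) gives the nearest description of the intended test: "Mixed between within subjects ANOVA will be conducted in a 2 (pre vs post ET) design to assess efficiency of the program". It continues: "When a significant interaction is observed, t tests, or Wilcoxon signed-rank tests will be used to determine where the interaction occurred". It also says "Statistical significance will be set at an alpha level of 0.05", again without sidedness. The Purpose section words the hypothesis directionally ("so that there could be greater adaptations, leading to higher increases in" the outcomes under periodized training), but no one-sided test is declared anywhere.

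**The concern.** Dropout is listed among the inputs, so 50 has to be read as the number randomised. Losing 37% of 50 leaves about 32 people, which looks too few to detect a standardised difference of 3/3.5 = 0.857 with 80% power.

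What is at stake is how a null result would be read. The paragraph tells the reader that a true difference of 3 ml/kg/min would be missed one time in five. If the real figure is nearer one in three, a non-significant VO2 peak comparison is weaker evidence against a clinically important difference than the plan claims.

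**Working it through.** **Inputs** (Methods, Participants): difference 3, SD 3.5, alpha 0.05, power 0.80, dropout 0.37, 25 per group. Standardised difference d = 3/3.5 = 0.857.

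**Test.** With two groups and two time points, the group-by-time interaction F test in Section 13 is identical to a two-sided t test on change. Two-sided is therefore the natural reading. One-sided results are shown as well because the hypothesis is directional.

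**Formula.** For n completers per group, power comes from the noncentral t distribution with df = 2n - 2 and noncentrality d × √(n/2).

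**Step 1: can 50 be reproduced?** Find the smallest n with power of at least 0.80, then divide by 1 - 0.37 = 0.63.

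| | Completers needed per group | Power | Randomised per group | Total |
|---|---|---|---|---|
| Two-sided | 23 (22 gives 0.793) | 0.811 | 23/0.63 = 36.5, so 37 | 74 |
| One-sided | 18 (17 gives 0.788) | 0.809 | 18/0.63 = 28.6, so 29 | 58 |

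Neither gives 50. The normal approximation gives 70 and 54, so it does not either. Reading 50 as the number of completers does not help: 25 per group gives 84.4% two-sided, more than the 23 needed, and it would leave the stated dropout unused.

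One route that does reach 50 is a one-sided test with dropout applied by multiplication: 36 × 1.37 = 49.3. That is an inference about where the figure came from, and nothing below depends on it.

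**Step 2: power with 50 randomised.** Completers = 50 × 0.63 = 31.5, or 15.75 per group.

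| Completers per group | Noncentrality | Two-sided power | One-sided power | Difference detectable at 80% (two-sided / one-sided) |
|---|---|---|---|---|
| 15 | 0.857 × √7.5 = 2.347 | 62.0% | 74.1% | 3.71 / 3.26 |
| 16 | 0.857 × √8 = 2.424 | 65.0% | 76.6% | 3.58 / 3.15 |

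**Step 3: dropout that 50 can absorb.** Two-sided 1 - 46/50 = 8%; one-sided 1 - 36/50 = 28%. The plan expects 37%.

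**Step 4: sensitivity to the meaning of the SD.** Step 2 applies if 3.5 is the SD of change, or if baseline is ignored. If 3.5 is instead the SD of VO2 peak itself, power depends on the baseline-to-follow-up correlation r. The plan gives no r, so the values below are assumptions. The SD of change is 3.5 × √(2(1 - r)). The baseline-adjusted SD is 3.5 × √(1 - r²), with one fewer degree of freedom. Two-sided, 16 per group:

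| r (assumed) | Change (the planned interaction) | Baseline-adjusted |
|---|---|---|
| 0.3 | 51% | 69% |
| 0.5 | 65% | 77% |
| 0.6 | 75% | 83% |
| 0.7 | 86% | 91% |
| 0.8 | 96% | 97% |

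Reaching 80% needs r of at least 0.65 (change) or 0.55 (baseline-adjusted) with 16 per group, and 0.67 or 0.59 with 15 per group.

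**The case against.** The strongest objection is that the five inputs do not fix a sample size until a test is chosen, and the paragraph names none. There are four assessments, and Section 13 also plans a repeated-measures mixed model across them. A two-sided between-group F test averaged over four visits needs 30 completers at an assumed correlation of 0.5, and 32 at 0.6. Divided correctly by 0.63 these give 48 and 51 randomised, close to 50. If 3.5 is the SD of a single measurement and the correlation is high, the planned interaction test also passes 80%. A mixed model could, in addition, use visits from participants who later leave.

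Part of this stands. The origin of 50 cannot be determined, and a multiplication error is only one possibility. Power above 80% is attainable under some correlations.

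It does not rescue the stated figure, for three reasons. Every such route needs a correlation that appears nowhere in the plan. The four-visit average includes baseline, where randomised groups have no expected difference, so it does not target the 12-month effect and is not the pre/post interaction that Section 13 describes. It is also fragile: with 32 completers its power falls to 76% at a correlation of 0.7 and to 72% at 0.8.

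**Conclusion.** The concern holds. On the documented inputs, 50 randomised with 37% dropout does not give 80% power in a two-group comparison of means under either sidedness. The shortfall is 15 to 18 percentage points two-sided and 3 to 6 one-sided. The chance of missing 3 ml/kg/min is 35-38% or 23-26%, against the stated 20%.

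This assumes a t test in completers, with 3.5 as the SD of the quantity compared and dropout spread evenly between groups. The arithmetic is certain under those assumptions. What remains open is whether the sponsor had a different test or a correlation in mind, and only the sponsor can say. No treatment estimate is biased. The point should be corrected because this paragraph is the plan's sole justification for its size.

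**What to change.** Rewrite the sample size paragraph and leave enrolment as it is.

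1. Name the test and say whether it is one- or two-sided.
2. Say whether 3.5 ml/kg/min is the SD of VO2 peak or of its change.
3. Allow for dropout by dividing by 1 - 0.37.
4. Report what 50 randomised supports. If the test is a two-sided t test in completers, the text could read: *With 50 randomised and 37% dropout, about 32 participants are expected to complete. A two-sided two-sample t test (alpha 0.05, SD 3.5) then has about 65% power for 3 ml/kg/min and 80% power for about 3.6 ml/kg/min.*
5. If a one-sided test was intended, declare it and report about 77%. If the calculation relied on repeated measures or baseline adjustment, state the assumed correlation, its basis and the resulting power, preferably over a range of correlations.

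The cost is one reworded paragraph and, unless a supporting correlation can be documented, a less favourable stated power.

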## STUDY DESIGN

A longitudinal RCT research design using two distinct ET prescriptions (periodization vs non periodization) will be applied in CVD patients. Briefly, following the informed consent process, patients will be randomized and stratified (by gender and age) to periodization or non periodization groups. The randomization code will be developed with a computer random-number generator to select random permuted blocks. Participants will exercise for a period of 12 months. All the same assessments, except the echocardiogram that will be done in M0 and M3 (for risk stratification), are going to be taken in 4 different time points during a year: M0 - baseline, M1 - 3 months after starting the ET, M2 - 6 months after starting the ET and M3 - 12 months after starting the ET. The patients will be randomized into either one of the two ET groups. Recruitment and screening will last 12 months (September 2017 to September 2018) and the patient assessment will last until September 2019. It is expected to finish the project with peer-review redaction submitted and/or accepted in December 2019.

The following assessments on the 4 time points will be performed at the Pulido Valente Hospital, FMH-UL and Academia de Fitness at EUL: Echocardiogram (Echo) (MyLab Alpha, ESAOTE); cardiopulmonary exercise test (CPET) (Ergostik, Geratherm Respiratory GmbH, Bad Kissingen); skeletal muscle deoxygenation dynamics (NIMO, Nirox srl); body composition - dual energy radiographic absorptiometry (DXA, Hologic Explorer-W); objective measured physical activity - accelerometer (ActiGraph GT3X+); functional physical fitness - Fullerton Functional Fitness Test; isometric strength – portable hand dynamometer JAMAR plus digital (Sammons Preston); maximal strength – 1RM and Quality of Life questionnaire.

All assessment moments will be done in 1 to 2 weeks:

Day 1 – Echo and CPET will be performed at the Pulido Valente Hospital;

Day 2 and 3 – during the day and time of the ET session at the EUL, the patient will perform: functional physical fitness tests; maximal strength; isometric strength and Quality of Life questionnaire;

Day 4 – In FMH, the dual energy radiographic absorptiometry (DXA) exam and the activation of the accelerometer to measure the objective measured physical activity will be done.

Day 5 – Submaximal CPET with the skeletal muscle deoxygenation dynamics at the Pulido Valente Hospital.

Individual reports will be sent by email or delivered on paper. During the 3-year project the multidisciplinary team will have bimonthly meetings to update the study information and discuss the patient's progress.

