# The Effect Of An Expanded Long Term Periodization Exercise Training In Patients With Cardiovascular Disease: Central And Peripheral Adaptations

## BACKGROUND

Cardiovascular Disease (CVD) remains the main cause of death in most European countries accounting for over four million deaths (47% of all deaths) each year. In Portugal CVD is among the main causes of morbidity, mortality and disability.

Cardiac Rehabilitation (CR) of patients with CVD has been practiced in Europe to varying degrees since the early 1970s. Coronary heart disease (CHD), if left untreated, is a progressive disease and individuals with CHD are at high risk for recurrent events. CR is a comprehensive, long-term program involving medical evaluation, prescribed exercise training (ET), cardiac risk factor modification, education and counselling. These programs are designed to limit the physiologic and psychological effects of cardiac illness, reduce the risk for sudden death or re-infarction, control cardiac symptoms, stabilize or reverse the atherosclerotic process, and enhance the psychosocial and vocational status of selected patients. Furthermore, it is a safe, useful and an effective treatment for patients with coronary artery disease (CAD), particularly after myocardial infarction (MI), but also for patients with cardiac interventions and chronic stable heart failure. Being a Class I recommendation from the American Heart Association, the American College of Cardiology, and the European Society of Cardiology, with exercise therapy consistently identified as a central element, guidelines recommend that patients with acute coronary syndromes should be offered comprehensive CR services in order to reduce risk factors that may have an impact on future cardiovascular complications.

Exercise adherence after a hospital-based CR program is reported to be poor with only 30% to 60% of those who complete a phase II CR program are still exercising 6 months later and after 12 months, up to 50 to 80% of participants failing to adhere to exercise. Despite the benefits associated with regular ET, adherence with supervised exercise-based CR remains low. More studies are needed to assess interventions that may help patients adhere to regular and effective ET after ending a hospital-based CR exercise program.

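### Programme efficiency is tested pre versus post training with 37% dropout expected, and the plan does not say that patients who stop training are still assessed or analysed in their allocated arm

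*Combined protocol and SAP*

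**What the plan says.** Statistical Analysis (section 13) names the test of the programme: "Mixed between within subjects ANOVA will be conducted in a 2 (pre vs post ET) design to assess efficiency of the program". It does not say which visit is the post value; I take it to be M3 (12 months). The same section plans a second analysis over M0 to M3, "General Linear Mixed Model Analysis for repeated measures with Tukey's posthoc procedure for the mean comparisons", and gives it the visit-to-visit comparisons rather than the efficiency test.

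The sample-size paragraph under Participants assumes "an expected dropout rate of 37" per cent. The figure is used only to enlarge the sample, and dropout is not defined.

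Study Design sets out a five-day schedule for each assessment. On Days 2 and 3, "during the day and time of the ET session at the EUL, the patient will perform: functional physical fitness tests; maximal strength", followed by handgrip and SF-36. The other measurements are made elsewhere: on Day 1 "Echo and CPET will be performed at the Pulido Valente Hospital", on Day 4 "In FMH, the dual energy radiographic absorptiometry (DXA) exam and the activation of the accelerometer", and on Day 5 the submaximal test at the hospital.

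Under Purpose, the primary endpoints of aim 1 include VO2 peak, 1RM and the DXA measures, and the list ends with "percentage of body fat mass, quality of life and functional physical fitness tests".

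The plan has no statement on assessing patients who stop training, no analysis population and no missing-data method.

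**The concern.** Stopping the training and leaving the study are different events, and the plan does not separate them. If a patient who stops is not measured at 12 months, a two-level pre/post ANOVA cannot use that patient. The efficiency result then describes those who remained, whereas randomisation protects only the comparison of everyone allocated.

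The reasons for stopping could differ by arm. The Exercise Training Program section takes the periodized arm to intervals above 90% of heart rate reserve at perceived exertion 17-19, against 40-75% of heart rate reserve in the other arm. The Background, on the other hand, suggests that repetitive steady-state exercise can become monotonous and harm adherence. Either arm could therefore lose its poorer responders, and the completer difference could be too large or too small. What is at stake is whether the trial can say what prescribing periodization does over 12 months.

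**Working it through.** **1. The plan's own figure.** Inputs from Participants: difference 3 ml/kg/min, SD 3.5, alpha 0.05, power 0.80, dropout 37%. Standardised difference = 3/3.5 = 0.857. Sidedness is not stated. A one-sided two-sample t test needs 18 per arm, and 18 x 1.37 = 24.7, rounded up to 25 per arm or 50 in total. The stated 50 reproduces this way. A two-sided t test needs 23 per arm before any allowance for dropout.

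**2. Patients at issue.** 0.37 x 25 = 9.25 per arm (18.5 of 50), leaving 15.75 per arm (31.5 of 50) if none of them has a 12-month value.

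**3. How selective loss shifts the comparison.** Let a fraction p of an arm stop, and let those patients change by D less than those who stay. The mean of all randomised in that arm is the completer mean minus D x p, so completers overstate the arm by D x p. The between-arm difference shifts by the gap between the two arms' values of D x p.

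Assumption, not in the documents: D = 3 ml/kg/min.

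- (a) Dropout 47% in one arm and 27% in the other (assumed): 3 x (0.47 - 0.27) = 0.6 ml/kg/min, which is 20% of the 3 ml/kg/min target.
- (b) Dropout 37% in both arms but selective in one only (assumed): 3 x 0.37 = 1.11 ml/kg/min, which is 37% of the target.
- (c) Dropout unrelated to outcome: D = 0, shift 0.

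The sign depends on which arm has the heavier or the selective loss.

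**4. Effect on the type I error.** SE of the completer difference = 3.5 x sqrt(2/15.75) = 1.25, with 2 x 15.75 - 2 = 29.5 degrees of freedom. For a two-sided 5% t test under a true null, the noncentrality is shift/SE:

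| Shift (ml/kg/min) | Shift/SE | Rejection of a true null |
|---|---|---|
| 0 | 0 | 5% |
| 0.6 | 0.48 | 7.5% |
| 1.11 | 0.89 | 13.8% |

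**5. Power with and without the patients who stop** (VO2 peak, t test, SD held at 3.5). If all 25 per arm are assessed and those who stop keep a fraction f of the effect, the expected difference is 3 x (0.63 + 0.37f).

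| Analysis | Difference (ml/kg/min) | Two-sided power | One-sided power |
|---|---|---|---|
| Completers, 15 to 16 per arm | 3 | 62-65% | 74-77% |
| All 25 per arm, f = 1 | 3.00 | 84% | 91% |
| All 25 per arm, f = 0.5 | 2.445 | 68% | 79% |
| All 25 per arm, f = 0 | 1.89 | 46% | 59% |

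The documents give no effect size or SD for 1RM, the functional tests or SF-36, so none of this can be computed for them.

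**The case against.** A reader might infer that the Days 2 and 3 slot leaves no way to measure a patient who has stopped, so that all 37% leave the 12-month comparison. The documents do not support that. The baseline assessment follows the same five-day schedule, yet the later visits are dated from the start of training, so the slot has to work for people not yet training. The wording can mean a time slot rather than testing within a workout. The four visits are fixed by months since starting, with no condition of still training, and nothing bars a patient who has stopped from attending. VO2 peak, DXA and the submaximal test are done outside the slot in any case.

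A reader might also infer that the bias favours periodization. The documents do not fix the direction. The monotony argument points to loss in the other arm, and the Background also reports that interval and resistance training have not been shown to compromise adherence. Table 2 matches the daily aerobic load totals at 520 in each arm, and the hardest intervals fall in 30 of its 135 sessions (46-60 and 106-120), with 4 x 2 = 8 work minutes each. The Background figure ("after 12 months, up to 50 to 80% of participants failing to adhere to exercise") describes patients after hospital rehabilitation has ended, not supervised training three times a week, so it cannot stand in for this trial's 37%.

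Finally, the planned mixed model over M0 to M3 can use the earlier visits of patients with no 12-month value.

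All of this stands, and it limits the claim. It does not close the gap. The efficiency test is assigned to the pre/post ANOVA, the mixed model cannot supply 12-month values that were never observed, and no sentence commits the site to collecting them.

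**Conclusion.** The concern holds as a gap in follow-up and analysis that affects every primary endpoint. As written, the efficiency comparison is likely to consist mainly of completers, and it is biased, in either direction, if the reasons for stopping differ by arm. The session slot adds to the risk for 1RM, functional tests and SF-36 but is not its sole cause.

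The size is illustrative and applies to VO2 peak only: a shift of 0.6 to 1.1 ml/kg/min, and rejection of a true null in about 7.5% to 14% of trials instead of 5%. It rests on three things that the documents do not give: a 3 ml/kg/min smaller change in those who stop, the assumed dropout patterns, and no 12-month value for any of the 37%. The figures should not be carried over to strength, function or quality of life.

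**What to change.** **Study Design.** State that stopping training is not leaving the study. Invite every randomised patient who has not withdrawn consent to M1, M2 and M3 at the calendar date. Offer Days 2 and 3 as an assessment appointment to those without a session; if burden is a concern, the minimum set is CPET and SF-36 at M3. Record the date and reason for stopping and tabulate them by arm. Under Participants, say which event the 37% refers to.

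**Statistical Analysis.** Make the between-arm efficiency test the group-by-visit contrast at M3 from the four-visit mixed model already named. Include all randomised patients in their allocated arm with every available visit, and state the missing-data assumption. Keep the pre/post ANOVA in completers as a labelled secondary analysis.

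**Cost.** Protocol wording, and out-of-session appointments for up to about 18 patients, using tests and staff already planned for everyone. Some of those who stop will decline. The all-randomised difference may also be smaller than the completer difference: full assessment raises two-sided power to about 84% if those who stop keep the whole effect and leaves it near 68% if they keep half, but lowers it to about 46% if they keep none, against 62-65% for completers at the full effect. That loss should be accepted knowingly, because it belongs to the question of what prescribing the regimen achieves. Twelve-month values not collected in their window cannot be recovered later.
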